Communication and Activation in Pain to
Enhance Relationships and Treat Pain
with Equity (COOPERATE)

NCT03562793

October 1, 2021

Statistical Analysis Plan

D7. STATISTICAL CONSIDERATIONS

D7a. Sample size and power. Our sample size is calculated based on estimated differences of intervention effects between the intervention and control arms on the primary outcome, patient activation (PAM), which is a continuous measure. In [name] pilot study with Veterans with chronic pain,⁸² we found a pre-treatment PAM score of 41.22 (std dev = 5.69) and a post-treatment score of 44.0 (std dev = 5.58), which represents a .49 standard deviation change in patient activation ($d = .49$) in response to a peer intervention for chronic pain. To be conservative, we are powering COOPERATE on a medium effect size of .40. To detect a .40 effect size based on a two-sample independent t-test with type I error =.05 and 80% power, 100 patients per group ($N = 200$) are required. Although our prior pain studies have had low attrition rates (<15%), we will conservatively plan for an attrition rate of 20%, which requires $N = 250$ (200/.80), or 125 patients per group. For secondary outcomes of COOPERATE, we estimated standardized effect sizes (difference in mean change from baseline between treatment groups divided by the pooled SD at baseline) for pain (BPI total) and anxiety (GAD-7) to be .69 and .40, respectively – these estimates were based on data from the SCAMP trial which involved phone-delivered pain self-management.⁹³ In COOPERATE, with a similarly delivered behavioral intervention and a sample size of 100 patients per arm, we will have 98.8% and 59.1% power to detect effect sizes of this magnitude for BPI total and GAD-7 based on a two-sample independent t-test with type I error set at .01 (assuming 5 clinical outcomes adjusted for multiple comparisons with a Šídák adjustment), which provides similar power to our contrast of interest from the linear mixed model. For other secondary outcomes (communication self-efficacy, depression, and pain coping), with a sample size of 200, we have 82.4% power to detect medium effect sizes (.50 SD difference), even after adjusting for multiple comparisons.

D7b. Randomization. Participants will be randomly assigned to one of the two study arms using random numbers generated by our statistician, [name]. Randomization with block sizes of 4 and 8 will be executed to ensure balance.

D7c. Data Analysis: Baseline Comparability. Because of the size of this study, we expect randomization will produce intervention and control groups that are comparable and balanced. However, we will tabulate baseline characteristics of participants and assess for potential imbalance in variables such as demographics, patient activation, communication self-efficacy, and pain severity between study arms. Continuous variables will be assessed with summary statistics (means, standard deviation, range, etc.). Frequency distributions will be calculated for categorical data. Appropriate tests, such as t-tests and chi-square, will be performed to determine whether there are differences between the two groups on these potential baseline covariates and, if so, these variables will be included in subsequent analyses. In all statistical analyses described below, we will employ an intent-to-treat (ITT) analysis.

D7d. Missing Data. We conservatively anticipate 20% attrition, which is reflected in our sample size. We will compare patient demographics between those who withdraw and those who participate to determine any discriminating characteristics. The proposed mixed model is appropriate if data are missing completely at random or missing at random. If data are missing not at random, we will use appropriate models (i.e., selection models,⁹⁴ pattern mixture models⁹⁵) to account for the missing data mechanism.

D7e. Data Analysis for Aim 1: Test effects of COOPERATE on key Veteran outcomes: patient activation (primary outcome), communication self-efficacy, pain intensity/interference, and psychological functioning.

All outcomes will be collected at baseline, 3, 6, and 9 months. A linear mixed-model repeated measures approach will be used to test the hypothesis in Aim 1 that COOPERATE will improve the primary outcome of patient activation (PAM) compared to the control condition at the 3-month time point. Fixed effects will include treatment, time (as categorical), and treatment X time interaction. We will examine the associations among the repeated measures within subjects and determine the appropriate variance-covariance structure. Our primary contrast of interest will be the group difference in change from baseline at the 3-month time point. Group differences in change from baseline at other time points (6-month and 9-month) will also be estimated. Covariates found to significantly differ between treatment and control groups at baseline will be included in the models. All analyses will include checking of assumptions and model fit. Working alliance, which is a key indicator of the quality of the patient-provider relationship, will serve as a baseline covariate in all models. Other potential covariates include physical and psychological comorbidities, patient-provider race and gender concordance, and patient-provider relationship length. Since patient activation and number of provider visits could influence one another, we will use number of visits during the prior year as a baseline covariate (if imbalanced between study arms), and will run a sensitivity analysis in which we re-run the final models for primary and secondary outcomes while adjusting for number of visits during the intervention period. Additionally, adherence to the intervention as measured by the number of sessions attended will be assessed for its dose-response effects on the primary and secondary outcomes.

Secondary outcomes of communication self-efficacy, total BPI (as well as BPI subscales: pain intensity and pain interference), and psychological functioning (depression, anxiety, and coping), will all be analyzed with the same mixed model approach as for the primary outcome. Because there are a number of secondary outcomes in Aim 1, we will use the Šídák method to adjust for multiple comparisons.

**Communication and Activation in Pain to
Enhance Relationships and Treat Pain with
Equity (COOPERATE)**

**[name]
Richard L. Roudebush VAMC
[name]
[name]**

Table of Contents:

Study Schema

- 1.0 Background**
- 2.0 Rationale and Specific Aims**

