5.0 Study Procedures

Intervention

Veterans randomized to the intervention will participate in the COOPERATE intervention. The intervention consists of 6 total sessions delivered individually over 12 weeks: 4 sessions focused on teaching skills related to goal clarification/prioritization and

communication (approximately 30-minutes each), delivered weekly for the first 4 weeks, plus 2 booster sessions (approximately 20-25 minutes each) delivered once per month for the next 2 months. All intervention sessions will be delivered by study team “coaches” via phone, audio-recorded, and a random subset reviewed for fidelity and quality. Coaches will be trained and supervised by [name] and co-investigators. Coach adherence checklists completed by trained study staff will be used. During regular supervision meetings, adherence and fidelity will be discussed. Role-play will be used to reinforce and correct deviations from study procedures.

Attention Control

Veterans randomized to the control group will receive phone calls on the same schedule as intervention Veterans. During these phone calls, study staff will ask Veterans a series of questions about their pain, self-management activities, and any changes they have experienced since the last call. These phone calls are designed to control for attention only, and Veterans will not be offered specific information or advice about their pain or its management (with the exception of suggesting a doctor visit if warranted).

Qualitative Interviews

Veterans

A subset of intervention patients will be selected for a qualitative interview at 6 months to better understand patient experiences with the intervention, including barriers, facilitators, and other factors that might affect implementation of COOPERATE. Veterans will be purposefully sampled using maximum variation sampling, a qualitative sampling strategy to obtain the broadest range of perspectives, purposefully challenging investigators’ preconceived understandings of the phenomenon under study and thus helping to elucidate the diversity of participants’ experiences.

Clinicians

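### D7a calls the .40 effect size for PAM conservative, but its only PAM evidence is one group's pre-to-post change of .49 SD, with no control-arm change reported or assumed

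*Combined protocol and SAP*

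**What the plan says.** SAP section D7a opens: "Our sample size is calculated based on estimated differences of intervention effects between the intervention and control arms on the primary outcome". The evidence that follows comes from a pilot in which PAM was 41.22 (SD 5.69) before treatment and 44.0 (SD 5.58) afterwards, a result "which represents a .49 standard deviation change in patient activation". The next step is "To be conservative, we are powering COOPERATE on a medium effect size of .40", applied "based on a two-sample independent t-test with type I error =.05 and 80% power". This gives 100 per group, and 125 per group after allowing for 20% attrition.

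Later in the same paragraph, the standardized effects for pain and anxiety are defined as differences between treatment groups in mean change from baseline. The PAM effect has no such definition.

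SAP section D7e and protocol section 8.0 make the primary contrast the group difference in change from baseline to 3 months, from a linear mixed model. D7c and D7e add a covariate when a baseline test shows imbalance, and patient activation is among the variables D7c would test. Protocol section 8.0 repeats N = 250 without an effect size.

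Under protocol section 5.0 (Attention Control), control Veterans are called on the same schedule as the intervention arm, and staff "ask Veterans a series of questions about their pain, self-management activities, and any changes they have experienced since the last call". They are given no specific information or advice about pain or its management.

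**The concern.** A one-group change includes whatever would have happened without the intervention, such as the effects of time, repeated measurement and contact. A between-arm difference has the control arm's change taken out. D7a moves from the first kind of figure to the second by trimming .49 to .40, and does not say what control-arm change it has in mind. The trim can be called conservative only relative to a within-group figure, which is not the quantity that the two-sample test addresses.

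The 80% figure is the plan's main statement of what the trial can detect. If a reader takes .40 as a cautious between-arm estimate, a non-significant PAM result could be read as stronger evidence against the intervention than the plan's own inputs allow.

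**Working it through.** **Inputs from D7a.** Pilot PAM 41.22 (SD 5.69) to 44.0 (SD 5.58); design effect .40; type I error .05; 80% power; 100 evaluable per arm; 20% attrition. The test's sidedness is not stated. Two-sided is assumed here, because a one-sided test would need only 78 per arm.

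**Inputs the documents do not give.** The control-arm PAM change g and the baseline to 3-month correlation r. Both are varied below. The intervention arm is assumed to repeat the pilot's .49 SD.

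**1. The plan's own figures.**
- Power = P(|T| > 1.972), where T is noncentral t with 198 degrees of freedom and noncentrality d × √(100/2). At d = .40 the noncentrality is 2.83 and power is 80.4%.
- The normal approximation needs 99 per arm.
- 200/.80 = 250.
- Pilot change: 44.0 − 41.22 = 2.78, and 2.78/5.69 = .489.
- The design effect in points: .40 × 5.69 = 2.28.

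All of D7a's PAM figures reproduce.

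**2. Between-arm effect if the pilot gain is repeated.** d = .49 − g. With 100 per arm, 80% power needs d = .398, so g can be at most .49 − .398 = .092 SD, or .092 × 5.69 = 0.52 points. This limit applies only under the assumed .49, and moves one for one with it.

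**3. Dependence on the correlation.** The planned contrast is a difference in change. As an approximation, take a simple change score with equal SDs. Its SD is √(2(1 − r)) in baseline SD units: 1.183 at r = .3, 1.000 at r = .5 and .775 at r = .7. The effect entering the power formula is d divided by that value. At r = .5 this equals D7a's t-test on the raw scale.

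**4. Baseline adjustment.** The effect entering the formula becomes d/√(1 − r²). At r = .5 the divisor is .866, so .34 becomes .393 and .29 becomes .335.

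Power with 100 per arm:

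| Control gain g (SD) | d | Change score, r = .3 | Change score, r = .5 | Change score, r = .7 | Baseline-adjusted, r = .5 |
|---|---|---|---|---|---|
| 0 | .49 | 83% | 93% | 99% | 98% |
| 0.05 | .44 | 74% | 87% | 98% | 95% |
| 0.09 | .40 | 66% | 80% | 95% | 90% |
| 0.15 | .34 | 52% | 67% | 87% | 79% |
| 0.20 | .29 | 41% | 53% | 75% | 65% |
| 0.25 | .24 | 30% | 39% | 59% | 50% |

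**The case against.** The strongest reply is that D7a claims only 80% power to detect .40, and that claim is true for any pair of arm changes that differ by .40. If the intervention arm gained .60 SD, controls could gain .20 SD and the power would be as stated. This stands. A reader might infer that the 80% is wrong, or that it fails once controls gain more than 0.09 SD. The documents support neither, because that limit also needs an intervention gain of exactly .49 SD and a correlation near .5. With a change score it is about 0.02 SD at r = .3 and 0.18 SD at r = .7. With no attrition (125 per arm) the t-test limit is about 0.13 SD.

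It can also be said that the control gain may be small. The calls teach no skills and offer no advice, and section 3.0 sets no PAM threshold for entry that would build in regression to the mean. That is fair, and no document supports any particular gain. It does not supply the missing between-arm estimate, though. The design uses an attention control precisely because contact might have an effect of its own.

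Two further inferences should be resisted. D7a reports one group's values but does not describe the pilot's design, so the pilot cannot be said to have lacked a comparator. D7a also describes the pilot as a peer intervention, while section 5.0 has study-team coaches deliver COOPERATE. The section 5.0 Timeline, however, refers to recruiting and training peer coaches, so the documents do not establish that the two programmes differ in this way.

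Finally, section 5.0 records that all baseline assessments were complete by 10/25/21, so the sample size is settled. That limits what the point can change to description, analysis and interpretation.

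**Conclusion.** The point holds as a gap in justification. D7a's stated between-arm basis for PAM is not shown, and calling .40 conservative is unsupported. The power calculation is correct at a true difference of .40 SD, and no power shortfall has been demonstrated.

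The possible consequence is material. On the plan's own pilot figure, power runs from 93% with no control gain to 39% with a gain of 0.25 SD at r = .5. At a gain of 0.20 SD it runs from 41% to 75% as r goes from .3 to .7. These figures rest on a repeated .49 SD gain, 100 evaluable per arm, a two-sided test, and a change-score approximation to the mixed model. The control gains and correlations are assumptions.

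Part of any loss can be recovered from data already collected, because the plan now adjusts for baseline PAM only if a test finds imbalance.

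**What to change.** **D7a.** Remove the description of .40 as conservative. Say that .49 is a within-group change and that no between-arm PAM estimate is given. State that 80% power applies to a true between-arm difference of .40 SD (about 2.3 points at SD 5.69) with 100 per arm. Show power over control gains of 0 to 0.25 SD and a range of correlations, including the favourable cases.

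**D7e and protocol section 8.0.** Make the 3-month contrast baseline-adjusted regardless of any imbalance test. Use either a constrained-baseline mixed model, or baseline PAM as a covariate with only post-baseline values as outcomes. Settle this before outcomes are compared by arm.

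**Interpretation.** Read a non-significant result from its confidence interval. Do not treat 2.3 points as an established meaningful difference, because no document gives it that status.

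**Cost.** SAP and protocol wording, a short power table and a change to the model specification. The stated power becomes conditional and less favourable. No extra patients, visits or data are needed.

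### Adjustment of the primary 3-month PAM contrast for baseline PAM is left to an imbalance test; pre-specifying it would gain precision at no cost in data

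*Combined protocol and SAP*

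**What the plan says.** SAP D7e fits a repeated-measures mixed model to PAM at baseline, 3, 6 and 9 months: "Fixed effects will include treatment, time (as categorical), and treatment X time interaction". The primary test is then fixed: "Our primary contrast of interest will be the group difference in change from baseline at the 3-month time point". Protocol section 8.0 repeats the model and the contrast.

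On covariates, D7c names patient activation among the variables to be compared between arms, and tests "whether there are differences between the two groups on these potential baseline covariates and, if so, these variables will be included in subsequent analyses". D7e and section 8.0 restate the rule: "Covariates found to significantly differ between treatment and control groups at baseline will be included in the models". No significance level is given for this screen. The one baseline covariate fixed in advance is working alliance, which "will serve as a baseline covariate in all models". Neither document pre-specifies baseline PAM as a covariate or a common baseline mean for the two arms.

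On power, D7a uses a plain two-sample t-test with 100 per arm and an effect of .40. The pilot change behind it is described in these words: "which represents a .49 standard deviation change in patient activation". For BPI and GAD-7 the effect is defined as the "difference in mean change from baseline between treatment groups divided by the pooled SD at baseline", and the t-test is said to be one "which provides similar power to our contrast of interest from the linear mixed model".

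**The concern.** With treatment, time and treatment-by-time all free, each arm keeps its own baseline mean. With complete data the 3-month contrast is then simply the difference in mean change scores. A change score takes off the whole baseline value, whereas the best predictor of the 3-month value takes off only r times the baseline (with equal SDs). The excess subtraction is noise, and it is largest when r is low.

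The imbalance rule does not repair this. At .05 it triggers in about one trial in twenty, because randomisation makes any imbalance a matter of chance. When it does trigger and baseline PAM enters as a main effect, the treatment-by-time contrast does not move in complete data, since a time-constant term cancels out of a change.

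At stake is precision on the single primary test, from a value every participant already supplies. Section 5.0 (Participant Payments) records that all baseline assessments were complete by 10/25/21, so further precision can come only from retention or from the analysis. D7a's statement that the t-test and mixed-model powers are similar also cannot be checked, because it depends on an r that is not given.

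**Working it through.** **Inputs from the documents.** 125 randomised per arm; 20% attrition, so 125 × .80 = 100 three-month values per arm; effect .40 SD; alpha .05 (.01 for secondary outcomes); pilot PAM SD 5.69 before and 5.58 after (D7a).

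**Assumptions.** Two-sided tests (this reproduces D7a); equal SDs at baseline and 3 months; r of .3 to .7.

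**1. Reproducing D7a.** Noncentral t, 198 df, 100 per arm, noncentrality d × √50:

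| d | alpha | power |
|---|---|---|
| .40 | .05 | 80.4% |
| .40 | .01 | 59.1% |
| .69 | .01 | 98.8% |
| .50 | .01 | 82.4% |

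All agree with the stated figures, and 200/.80 = 250.

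**2. Variance per arm, in SD² units** (n0 = 125 baseline, n3 = 100 three-month values):

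- planned change contrast: (1 − r²)/n3 + (1 − r)²/n0
- baseline-adjusted contrast: (1 − r²)/n3

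At r = .5: planned .75/100 + .25/125 = .0095; adjusted .0075; saving .0020/.0095 = 21%. The planned form already credits the mixed model with the baselines of participants who drop out.

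**3. Power for PAM at d = .40.** Noncentrality is d/√(2 × variance). At r = .5: .40/√.019 = 2.90 planned, .40/√.015 = 3.27 adjusted. The scale of the .40 is not stated. The pilot ratio (44.0 − 41.22)/5.69 = .49 points to raw-score SD. If it were in change-score SD units, the raw effect would be .40 × √(2(1 − r)).

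| r | variance saved | raw SD: planned → adjusted | change SD: planned → adjusted | 95% CI half-width, PAM points (SD 5.69): planned → adjusted |
|---|---|---|---|---|
| .3 | 30% | 69.4 → 83.9% | 83 → 94% | 1.81 → 1.51 |
| .4 | 26% | 75.5 → 86.7% | 83 → 92% | 1.69 → 1.45 |
| .5 | 21% | 82.3 → 90.1% | 82 → 90% | 1.55 → 1.37 |
| .6 | 17% | 89.5 → 94.0% | 82 → 88% | 1.39 → 1.27 |
| .7 | 12% | 95.8 → 97.6% | 82 → 86% | 1.21 → 1.13 |

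On the raw scale the planned contrast reaches 80% only at r of about .47 with 20% attrition, .44 with 15% and .37 with none.

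**4. What holds without knowing r.** The adjusted noncentrality is .40 × √(50/(1 − r²)) on the raw scale and .40 × √(100/(1 + r)) on the change scale. For r from 0 to 1 both are at least .40 × √50, the t-test value. The D7a power is therefore a lower bound for the adjusted contrast.

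**5. Precision expressed as enrolment.** To match the *adjusted* precision (not to reach 80% power), the planned contrast needs N per arm solving (1 − r²)/(.8N) + (1 − r)²/N = (1 − r²)/100. At r = .5: (.9375 + .25)/N = .0075, so N = 158. For r = .3/.4/.5/.6/.7, N is about 179/168/158/150/143, against 125.

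**6. Does the imbalance rule recover the loss?** Simulation with 100 complete pairs per arm and 20,000 trials per r, with full adjustment for baseline PAM whenever a .05 screen triggers:

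| r | never adjusted | adjusted if imbalanced | always adjusted |
|---|---|---|---|
| .3 | 66.1% | 67.4% | 83.3% |
| .5 | 80.6% | 81.8% | 90.1% |
| .7 | 95.4% | 95.6% | 97.6% |

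Under the null the conditional rule rejects in 3.9 to 4.6% of trials, so error is not inflated. With baseline PAM added only as a main effect to the four-visit model (complete data, N = 250), the treatment × 3-month estimate was the same to four decimals with and without it.

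**7. The similar-power statement in D7a.** Planned contrast at alpha .01, r = .3/.4/.5/.6/.7: GAD-7 (d = .40) 45/53/62/73/86%, against 59.1% stated; BPI (d = .69) 95/98/99/99.8/100%, against 98.8%. The statement depends materially on r for GAD-7 and hardly at all for BPI.

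**The case against.** The strongest reply is that nothing here is an error. The change contrast is valid, holds its type I error, and matches Aim 1, which is worded in terms of increases. The size of the gain rests on an r that the documents do not give. From about r = .47 upward on the raw scale, and at every r tabulated on the change scale, the plan meets its 80%; at r = .8 the raw-scale gain is only 99.4% to 99.7%. All of that stands, and it is why this is an efficiency point and not a power deficit.

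Three technical qualifications also stand in part.

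- The saving depends on the SD ratio, being proportional to (1 − r × SD3/SD0)². It vanishes at, for example, a ratio of 1.25 with r = .8. The pilot ratio is 5.58/5.69 = .98, which keeps it positive for every r below 1.
- The main-effect result is exact only in complete data. With 20% of follow-up missing, adding baseline PAM moved the estimate in one check (.422 to .445 at r = .3) but did not improve its standard error.
- The SAP does not say outright whether baseline PAM is a response or is subtracted. If it is subtracted, entering baseline PAM would be a real adjustment, but still only when the screen triggers; step 6 shows how little that recovers.

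Finally, the remedy alters the primary contrast late in the trial. That calls for care with timing, not for leaving the contrast as it is.

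**Conclusion.** The point holds as an improvement the sponsor should make. The plan does not secure adjustment of its primary contrast for baseline PAM, and the imbalance rule is no substitute. With equal SDs, 125 baseline and 100 three-month values per arm, and r assumed between .3 and .7, pre-specified adjustment removes 30% to 12% of the variance. The gain in power is 14 to 2 percentage points if the .40 is in raw-score SD units, and 11 to 5 points if it is in change-score SD units. No shortfall against 80% is demonstrated. The firm result is that adjustment makes the stated 80% safe against both unknowns, r and the scale of the effect. On the raw-score scale the planned contrast lacks that protection below r of about .47. The quantity estimated does not change: under randomisation the 3-month difference and the difference in change have the same expectation.

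**What to change.** In SAP D7e and protocol section 8.0, pre-specify baseline adjustment for PAM and for each secondary outcome, whatever the D7c comparison shows. Two forms will do:

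- a mixed model with a common baseline mean for the arms (time plus treatment-by-follow-up-time terms, no treatment effect at baseline); or
- a model of the 3-, 6- and 9-month values with the baseline value and its interaction with time as covariates.

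Use one form only, so that baseline PAM is not both response and covariate. The common-mean form requires that baseline PAM was measured before allocation was known. The documents do not state that order; D7e should. If the order did not hold, neither form should be adopted without further thought.

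Name the adjusted 3-month difference as the primary contrast, keep working alliance as a covariate, and keep the planned change contrast as a sensitivity analysis. In D7a, state the SD scale of the .40, and either the assumed r or that the t-test power is a lower bound for the adjusted contrast when r is 0 or more.

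The cost is an amendment in two places, one sentence in D7a and a few lines of model code, with no new data or participants. Because all baselines and probably many 3-month values are already in, the amendment must be dated and fixed before outcomes are compared by arm. The documents do not show whether that comparison had taken place.

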1.0 Background

Chronic pain affects 40-70% of Veterans and amounts to over \$600 billion/year in direct medical costs and lost worker productivity. Racial disparities in pain treatment have been extensively documented. Minority patients, including Veterans, are more likely to be undertreated for pain. Minority Veterans have pain documented less frequently, undergo more urine drug tests, and are more likely to be referred for substance abuse evaluation than White Veterans. Compounding these pain care disparities, minority Veterans exhibit lower levels of patient activation than Whites. Patient activation—having knowledge, confidence, and skills to manage health—is associated with better health experiences, self-management, and outcomes. Low activation is frequently manifested in poorer communication among minority patients. Minority patients are less likely to share their concerns with providers, ask questions, and prepare for their clinic visits. This poor communication is associated with lower quality care, poorer patient-provider relationships, and treatment non-adherence. The poorer communication experienced by minorities is exacerbated by the documented difficulties in patient-provider communication about chronic pain and its treatment—particularly where opioids are concerned.

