Up to 35 clinicians who work with patients with chronic pain (e.g., psychologists, primary care physicians, rehabilitation physicians, nurses, physical therapists) will also participate in interviews. Questions directed toward clinicians will focus on institutional implementation, including facilitators and barriers to adoption of COOPERATE (“adoption”), challenges to delivering this intervention with fidelity (“implementation”), and the ability to sustain such a program within either primary care or the chronic pain clinic (“maintenance”). Interviews will take approximately 30-45 minutes.

All interviews will be one-on-one, face-to-face, and will take place in a private room in RVAMC. They will be conducted by research study staff, who have training and experience conducting qualitative interviews for [name]. Interviews will be audio-recorded, transcribed, and checked for accuracy.

During the COVID-19 crisis, qualitative interviews will be conducted over the phone.

Data Collection

The Data Manager will create and maintain all databases. To ensure quality, data will be entered by the RA and checked by another study team member. For qualitative data, transcribed interviews will be checked for accuracy, de-identified, and entered into NVivo. Each patient will be assigned a unique study ID number, and all data will be

entered into a password-protected database behind the VA firewall using these ID numbers.

Participant Payments

Participants will be paid \$40 for each assessment completed (baseline, 3 months, 6 months, and 9 months), for a total of \$160 per participant. Clinicians will not be compensated.

Due to a policy change in the VA Research and Development department regarding purchasing incentives, we are increasing the incentive from \$40 to \$50, which is a nominal increase of \$10. This is only for 3M, 6M and 9M assessments, as all the BL assessments have been completed as of 10/25/21.

Timeline

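### The planned dose-response analysis of sessions attended compares groups that were not randomised, and its result should be reported as an association rather than an effect.

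*Combined protocol and SAP*

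**What the plan says.** The analysis rests on one sentence at the end of the main paragraph of SAP section D7e: "adherence to the intervention as measured by the number of sessions attended will be assessed for its dose-response effects", for the primary and secondary outcomes. Protocol section 8.0 repeats the mixed-model plan but does not mention this analysis. The sentence does not say whether the control arm is included, whether control calls count as sessions, or how the result is to be interpreted.

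The surrounding text supplies some context:

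- The D7e paragraph sets up a linear mixed model with treatment, categorical time and their interaction, and states: "Our primary contrast of interest will be the group difference in change from baseline at the 3-month time point".
- Working alliance enters every model as a baseline covariate. Covariates that differ significantly between arms at baseline are added. Comorbidities, patient-provider concordance and length of relationship are listed as further candidates.
- SAP D7c applies intention-to-treat to all the analyses that follow it.
- Protocol section 5.0: "The intervention consists of 6 total sessions delivered individually over 12 weeks". For the comparator: "Veterans randomized to the control group will receive phone calls on the same schedule as intervention Veterans".
- SAP D7b and protocol section 4.0 randomise participants to arm and to nothing else.

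**The concern.** Attendance runs from 0 to 6 and accrues over the 12 weeks after randomisation. Veterans who complete all six sessions may differ from those who stop after two in ways that also bear on activation, pain or mood. Comparing outcomes across levels of attendance therefore loses the protection of randomisation, whatever D7c says about intention-to-treat.

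The protocol's background makes selection plausible: "This poor communication is associated with lower quality care, poorer patient-provider relationships, and treatment non-adherence". The same section describes poor communication as a common manifestation of low activation. Activation is the primary outcome and communication self-efficacy is a secondary outcome. D7e itself accepts that activation and provider visits may influence each other, but does not extend that caution to sessions.

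What is at stake is the interpretation of a supplementary result. If the association is reported as an effect, it could show a dose-response for an intervention that does nothing, or exaggerate, hide or reverse a real one.

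**Working it through.** **The plan's own figure.** The documents give no figure for this analysis. The only related design figure is the sample size in D7a. An exact two-sample t-test with effect size 0.40, two-sided 0.05 and 80% power needs 99.08, so 100 per arm (power 80.4%), and 200/0.80 = 250. It reproduces, and nothing below changes it.

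**Inputs to the illustration**

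- From D7a: a true arm effect of 0.40 SD and 100 patients analysed per arm.
- Assumed, not in the documents: mean sessions 4.85 and SD 1.71 in the intervention arm, outcome SD 1, the whole effect acting through sessions and linear in their number, and a selection correlation r between sessions and the outcome a patient would have had without them. Negative r means that patients who would do worse attend more.

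**True effect per session.** 0.40/4.85 = 0.0825 SD.

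**Expected slope within the intervention arm.** True effect plus selection = 0.0825 + r/1.71.

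| r | r/1.71 | Expected slope | Simulated mean (6,000 runs) |
|---|---|---|---|
| -0.3 | -0.175 | -0.093 | -0.093 |
| -0.2 | -0.117 | -0.034 | -0.034 |
| 0 | 0 | 0.082 | 0.081 |
| 0.2 | 0.117 | 0.199 | 0.199 |
| 0.3 | 0.175 | 0.258 | 0.258 |

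At r = 0.3 the slope is about three times the truth (0.258/0.0825 = 3.1). At r = -0.3 a real benefit appears as harm. With no intervention effect at all, the slope is r/1.71 alone, up to 0.175 SD per session in either direction.

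**Estimate based on randomised arm.** Difference in mean outcome divided by difference in mean COOPERATE sessions = 0.40/(4.85 - 0) = 0.0825. In the same simulations it averaged 0.082 to 0.083 at every r, with SD about 0.029. That stability follows from the imposed assumptions: assignment acts only through sessions, and linearly. If assignment instead had a direct effect of 0.1 or 0.2 SD and sessions did nothing, the estimate would be 0.1/4.85 = 0.021 or 0.2/4.85 = 0.041 per session, all of it spurious.

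**Dependence on assumed attendance.** With mean sessions of 3, 4 or 5.5, the same 0.40 SD becomes 0.133, 0.100 or 0.073 per session.

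**Control-arm comparison.** The standard error of one arm's slope is 1/(1.71 × √100) = 0.0585, so the standard error of a difference between arms is 0.0585 × √2 = 0.083. A true difference of 0.0825 is about one standard error, which gives about 17% power at two-sided 0.05. The comparison can only be an informal check.

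**The case against.** **Some adjustment is already planned.** Working alliance is in every model, and the background sentence on non-adherence also mentions poorer patient-provider relationships, of which working alliance is described as a key indicator. This stands as partial adjustment. Neither it nor covariates chosen for imbalance between arms was selected to predict attendance.

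**The evidence for selection is indirect.** The background sentence concerns communication with clinicians and adherence to treatment, not attendance at telephone coaching. This also stands. The sentence makes selection plausible and no more.

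**The numbers are assumed.** True. They show what selection of a given strength would do and say nothing about its strength in this trial.

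**The remedy answers a different question.** The instrumental-variable estimate largely rescales the intention-to-treat difference and cannot show the shape of a dose-response. This stands as a limit of the estimate. It does not justify reading the raw association as causal.

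Two stronger readings are tempting, and the documents do not support them:

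- A reader might infer that the outcome is wholly undefined, so that the sign could turn on using the 3-month level or the change. The sentence closes a paragraph whose contrast is change from baseline at 3 months, so carrying that over is the natural reading, though it is not explicit.
- A reader might extend the point to the plan to "re-run the final models for primary and secondary outcomes while adjusting for number of visits during the intervention period" and dismiss that sensitivity analysis as uninformative. With complete data, a main effect of visits that is constant over time does cancel from a change contrast. But the SAP expects dropout ("We conservatively anticipate 20% attrition, which is reflected in our sample size"). When dropout was simulated to depend on visits differently by arm, under assumed inputs, the re-run moved the 3-month contrast by 0.03 to 0.09 SD on average (up to 0.18), towards the true value. A visits-by-time term, which would change what is estimated, is not in the plan. No criticism of that re-run is made here.

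**Conclusion.** The point holds and is minor. As written, D7e would report a comparison by a non-randomised, post-randomisation variable as an effect on every outcome, with only partial baseline adjustment. That conclusion rests on the text alone.

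The size of the bias cannot be taken from the documents. Under the stated assumptions, a true 0.08 SD per session could appear as anything from about -0.09 to 0.26 for selection correlations between -0.3 and 0.3. A reader might also infer that the planned slope is bound to be too favourable. The documents give no direction for selection, so it could equally be too small.

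No stated aim depends on this analysis. The primary 3-month contrast, the sample size and the type I error are unaffected.

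**What to change.** Amend the sentence in D7e as follows.

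1. Call the sessions-outcome association exploratory and descriptive, and drop the word effects. Say that the intention-to-treat statement in D7c does not protect it.
2. State that the outcome is change from baseline, as in the rest of the paragraph, and whether the baseline value is adjusted for. State which arms are included and that control calls are not COOPERATE sessions.
3. Base any causal per-session statement on an instrumental-variable estimate, with randomised arm as instrument and COOPERATE sessions received (0 in control) as exposure. Declare its assumptions: assignment acts only through sessions, and the effect is linear in their number.
4. If completion of control calls has already been logged, show the same association in the attention-control arm as an informal check on selection. This assumes that selection is similar in both arms.

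The cost is SAP wording plus one short analysis if a causal statement is wanted. The instrumental-variable estimate is an average per-session effect, gives no information on the shape of a dose-response, and is wrong if assignment acts outside the sessions. The control-arm check may not be available: the protocol's payments text notes that "all the BL assessments have been completed as of 10/25/21", so calls that were not logged may not be recoverable.
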